#### 4.6 Dosing Delays

Pembrolizumab may be interrupted for situations other than treatment-related AEs such as medical / surgical events or logistical reasons not related to study therapy. Subjects should be placed back on study therapy within 3 weeks of the scheduled interruption, unless otherwise discussed with the Sponsor. The reason for interruption should be documented in the patient's study record. See Tables 2 and 4 for details.

**Table 4. Treatment Delays and Resumption of Therapy.**

5	Treatment held on the days of any local therapy to brain lesions	One week later
6	Suspicion of pregnancy	Resume if pregnancy ruled out
7	Treatment held during any hospitalization for illness	Resume after discharge from hospital
8	Treatment held on day of any general surgery	Resume 1 week later (if outpatient surgery) or after discharge from hospital (if hospitalization is required for recovery or complications)

#### 4.7 Duration of Therapy

In the absence of treatment delays due to adverse event(s), treatment may continue for up to 2 years or until one of the following criteria applies:

1	Disease progression (see Section 4.8)
2	Symptomatic deterioration of health status without objective evidence of disease progression. Every effort should be made to document objective progression of disease in such cases.
3	Imminent risk in the case of progressing lesion or new/worsening edema seen on brain MRI
4	Unmanageable toxicity most probably attributed to MK-3475 (see Table 2)
5	Development of intercurrent illness limiting the ability to comply with study or the development of uncontrolled concurrent illness that prevents further administration of treatment or confound the ability to interpret data
6	General or specific changes in the patient's condition rendering the patient unacceptable for further treatment in the judgment of the investigator
7	Patient request for discontinuation, patient withdrawal from study, or patient lost to follow up
8	Development of neurologic or systemic complications following local therapy to any lesion
9	Death
10	Study termination by sponsor

#### 4.8 Treatment Beyond Disease Progression

If radiologic imaging shows PD, tumor assessment should be repeated >4 weeks later in order to confirm PD with the option of continuing treatment while awaiting radiologic confirmation of progression. If repeat imaging shows a reduction in tumor burden compared to the initial scan demonstrating PD, treatment may be continued as per treatment calendar. If repeat imaging confirms progressive disease, subject will be discontinued from study therapy. Patients may continue treatment with MK-3475 beyond PD by RECIST 1.1 (in the body) or mRECIST in the brain, if they are determined by the investigator to be deriving clinical benefit from treatment and they continue to meet all other criteria for treatment. Patients who have rapid progression of disease or clinical deterioration will be removed from study. The decision to continue treatment beyond initial progression should be discussed with the medical monitor.

Additionally, in cases where the majority of the disease is stable or responding, and progressing lesions can be controlled with local therapy (ie resection or radiotherapy), the patient may be continued on trial following local therapy.

#### 4.9 Duration of Follow Up

Patients who discontinue early or who complete the study treatment period in full will be followed for survival after removal from study until death.

## 5 GENERAL CONCOMITANT THERAPY AND SUPPORTIVE CARE GUIDELINES

### 5.1 Concomitant Medication

Additional anti-tumor therapies are prohibited during study treatment. Additionally, the use of corticosteroids or other immunosuppressive medications will not be allowed during study therapy (unless used to treat a drug-related adverse event). Low-dose steroid use ( $\leq 10$  mg of prednisone or equivalent) as corticosteroid replacement therapy is allowed.

### 5.2 Local Therapy

#### Local therapy for brain metastases:

Local surgical therapy in the form of craniotomy or LITT will be performed on the surgical lesion(s) prior to initiating systemic therapy. At any time point throughout the study, local therapy (surgery, gamma knife or LITT) will be administered to a lesion that becomes clinically concerning if deemed necessary by the investigators. This can be followed by continuation on MK-3475, provided that the patient is otherwise benefiting from therapy and has stable disease or disease shrinkage in other lesions by RECIST criteria. Approval from the study PI or co-PIs is required to continue treating the patient on MK-3475. A brain metastasis that has been treated locally will not be considered evaluable for response and will not be included when calculating the sum of largest dimensions. If the treated lesion constitutes  $> 25\%$  of the target lesions (for example, if one of three target lesions is treated locally), this will be considered progressive disease. If  $> 75\%$  of the baseline lesions are not treated with local therapy and evaluable by imaging, the patient will be considered evaluable, and response for the primary endpoint analysis will be assessed based on the remaining lesions. Additional response evaluation will be performed which will consider those patients who require local therapy while on study as having PD at the time of local therapy.

#### Local therapy for extra-cerebral metastases:

Local surgery or radiation therapy (if indicated for palliative measures only after discussion with the study PI or co-PIs) may be permitted and the patient can continue to receive MK-3475 provided there is otherwise evidence of clinical benefit from treatment (i.e. stable disease or response in measurable lesions). The criteria applied for assessing brain metastasis response will be applied to extra-cerebral metastases as well.

### 5.3 Supportive Care Guidelines

Subjects should receive appropriate supportive care measures as deemed necessary by the treating investigator. Suggested supportive care measures for the management of AEs with potential immunologic etiology are outlined along with the dose modification guidelines in Table 2. Where appropriate, these guidelines include the use of oral or IV treatment with corticosteroids, as well as additional anti-inflammatory agents if symptoms do not improve with administration of corticosteroids. Note that several courses of steroid tapering may be necessary as symptoms may worsen when the steroid dose is decreased. For each disorder, attempts should be made to rule out other causes such as metastatic disease or bacterial or viral infection,

which might require additional supportive care. The treatment guidelines are intended to be applied when the Investigator determines the events to be related to pembrolizumab.

Note: If after the evaluation of the event, it is determined not to be related to pembrolizumab, the Investigator does not need to follow the treatment guidance. Refer to Table 2 for guidelines regarding dose modification and supportive care.

It may be necessary to perform conditional procedures such as bronchoscopy, endoscopy, or skin photography as part of evaluation of the event.

Management of Infusion Reactions: Acute infusion reactions (which can include cytokine release syndrome, angioedema, or anaphylaxis) are different from allergic/hypersensitive reactions, although some of the manifestations are common to both AEs. Signs and symptoms usually develop during or shortly after drug infusion and generally resolve completely within 24 hours of completion of infusion. Signs/symptoms may include: Allergic reaction/hypersensitivity (including drug fever); Arthralgia (joint pain); Bronchospasm; Cough; Dizziness; Dyspnea (shortness of breath); Fatigue (asthenia, lethargy, malaise); Headache; Hypertension; Hypotension; Myalgia (muscle pain); Nausea; Pruritis/itching; Rash/desquamation; Rigors/chills; Sweating (diaphoresis); Tachycardia; Tumor pain (onset or exacerbation of tumor pain due to treatment); Urticaria (hives, welts, wheals); Vomiting.

Table 4 below shows treatment guidelines for subjects who experience an infusion reaction associated with administration of MK-3475.

**Table 4. Infusion Reaction Treatment Guidelines**

NCI CTCAE Grade	Treatment	Premedication at subsequent dosing
Grade 1 Mild reaction; infusion interruption not indicated; intervention not indicated	Increase monitoring of vital signs as medically indicated until the subject is deemed medically stable in the opinion of the investigator.	None
Grade 2 Requires therapy or infusion interruption but responds promptly to symptomatic treatment (e.g., antihistamines, NSAIDs, narcotics, IV fluids); prophylactic medications indicated for <=24 hrs	Stop Infusion and Monitor Symptoms. Additional appropriate medical therapy may include but is not limited to: IV fluids Antihistamines NSAIDs Acetaminophen Narcotics  Increase monitoring of vital signs as medically indicated until the subject is deemed medically stable in the opinion of the investigator.	Subject may be premedicated 1.5h (± 30 minutes) prior to infusion of MK-3475 with:  Diphenhydramine 50 mg po (or equivalent dose of antihistamine).  Acetaminophen 500-1000 mg po (or equivalent dose of antipyretic).

NCI CTCAE Grade	Treatment	Premedication at subsequent dosing
	
If symptoms resolve within one hour of stopping drug infusion, the infusion may be restarted at 50% of the original infusion rate (e.g. from 100 mL/hr to 50 mL/hr). Otherwise dosing will be held until symptoms resolve and the subject should be premedicated for the next scheduled dose.
 
Subjects who develop Grade 2 toxicity despite adequate premedication should be permanently discontinued from further trial treatment administration.
	

Grades 3 or 4            Grade 3:            Prolonged (i.e., not rapidly responsive to symptomatic medication and/or brief interruption of infusion); recurrence of symptoms following initial improvement; hospitalization indicated for other clinical sequelae (e.g., renal impairment, pulmonary infiltrates)            Grade 4:            Life-threatening; pressor or ventilatory support indicated
	
Stop Infusion and Monitor Symptoms.            Additional appropriate medical therapy may include but is not limited to:
 
 
IV fluids
 
Antihistamines
 
NSAIDS
 
Acetaminophen
 
Narcotics
 
Oxygen
 
Pressors
 
Corticosteroids
 
Epinephrine
 
 
Increase monitoring of vital signs as medically indicated until the subject is deemed medically stable in the opinion of the investigator.            Hospitalization may be indicated.  Subject is permanently discontinued from further trial treatment administration.
	No subsequent dosing

Appropriate resuscitation equipment should be available in the room and a physician readily available during the period of drug administration.            For Further information, please refer to the Common Terminology Criteria for Adverse Events v4.0 (CTCAE) at http://ctep.cancer.gov
		

### 5.3.1 Supportive Care Guidelines for Events of Clinical Interest (ECIs) and Immune-related Adverse Events (irAEs)

Events of clinical interest of a potential immunologic etiology (irAEs) may be defined as an adverse event of unknown etiology, associated with drug exposure and is consistent with an immune phenomenon. irAEs may be predicted based on the nature of the MK-3475 compound, its mechanism of action, and reported experience with immunotherapies that have a similar mechanism of action. Special attention should be paid to AEs that may be suggestive

of potential irAEs. An irAE can occur shortly after the first dose or several months after the last dose of treatment.

If an irAE is suspected, efforts should be made to rule out neoplastic, infectious, metabolic, toxin or other etiologic causes prior to labeling an adverse event as an irAEs. Information on how to identify and evaluate irAEs has been developed and is included in the Immune-Related Adverse Event Guidance Document. Subjects who develop a Grade 2 or higher irAEs should be discussed immediately with the Merck Clinical Monitor.

Recommendations to managing irAEs not detailed elsewhere in the protocol are detailed in Table 5.

**Table 5 General Approach to Handling irAEs**

irAEs	Withhold/Discontinue MK-3475?	Supportive Care
Grade 1	No action	Provide symptomatic treatment
Grade 2	May withhold MK-3475	Consider systemic corticosteroids in addition to appropriate symptomatic treatment
Grade 3 and Grade 4	Withhold MK-3475  Discontinue if unable to reduce corticosteroid dose to < 10 mg per day prednisone equivalent within 12 weeks of toxicity	Systemic corticosteroids are indicated in addition to appropriate symptomatic treatment. May utilize 1 to 2 mg/kg prednisone or equivalent per day.  Steroid taper should be considered once symptoms improve to Grade 1 or less and tapered over at least 4 weeks.

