#### 4.5 MK-3475 Dosage and Administration

##### Trial Treatments

Drug	Dose/Potency	Dose Frequency	Route of Administration	Regimen/Treatment Period
MK-3475	10 mg/kg	Q2W	IV infusion	Day 1 of each cycle

AEs associated with pembrolizumab exposure may represent an immunologic etiology. These immune-related AEs (irAEs) may occur shortly after the first dose or several months after the last dose of pembrolizumab treatment and may affect more than one body system simultaneously. Therefore, early recognition and initiation of treatment is critical to reduce complications. Based on existing clinical trial data, most irAEs were reversible and could be managed with interruptions of pembrolizumab, administration of corticosteroids and/or other supportive care. For suspected irAEs, ensure adequate evaluation to confirm etiology or exclude other causes. Additional procedures or tests such as bronchoscopy, endoscopy, skin biopsy may be included as part of the evaluation. Based on the severity of irAEs, withhold or permanently discontinue pembrolizumab and administer corticosteroids. Dose modification and toxicity management guidelines for irAEs associated with pembrolizumab are provided in Table 2.

Table 2. Dose Modification Guidelines for Drug-Related Adverse Events

General instructions:				

 
1. Corticosteroid taper should be initiated upon AE improving to Grade 1 or less and continue to taper over at least 4 weeks.
 
2. For situations where pembrolizumab has been withheld, pembrolizumab can be resumed after AE has been reduced to Grade 1 or 0 and corticosteroid has been tapered. Pembrolizumab should be permanently discontinued if AE does not resolve within 12 weeks of last dose or corticosteroids cannot be reduced to <math>\leq 10</math> mg prednisone or equivalent per day within 12 weeks.
 
3. For severe and life-threatening irAEs, IV corticosteroid should be initiated first followed by oral steroid. Other immunosuppressive treatment should be initiated if irAEs cannot be controlled by corticosteroids.
 
				
Immune-related AEs	Toxicity grade or conditions (CTCAEv4.0)	Action taken to pembrolizumab	irAE management with corticosteroid and/or other therapies	Monitor and follow-up

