Hypophysitis	Grade 2	Withhold	
 
Administer corticosteroids and initiate hormonal replacements as clinically indicated.
 
	
 
Monitor for signs and symptoms of hypophysitis (including hypopituitarism and adrenal insufficiency)
 

	Grade 3 or 4	Withhold or permanently discontinue 		
Hyperthyroidism	Grade 2	Continue	
 
Treat with non-selective beta-blockers (eg, propranolol) or thionamides as appropriate
 
	
 
Monitor for signs and symptoms of thyroid disorders.
 

	Grade 3 or 4	Withhold or permanently discontinue 		
Hypothyroidism	Grade 2-4	Continue	
 
Initiate thyroid replacement hormones (eg, levothyroxine or liothyronine) per standard of care
 
	
 
Monitor for signs and symptoms of thyroid disorders.
 

Nephritis and Renal dysfunction	Grade 2	Withhold	
 
Administer corticosteroids (prednisone 1-2 mg/kg or equivalent) followed by taper.
 
	
 
Monitor changes of renal function
 

	Grade 3 or 4	Permanently discontinue		
Myocarditis	Grade 1 or 2	Withhold	
 
Based on severity of AE administer corticosteroids
 
	
 
Ensure adequate evaluation to confirm etiology and/or exclude other causes
 

	Grade 3 or 4	Permanently discontinue		
All other immune-related AEs	Intolerable/persistent Grade 2	Withhold	
 
Based on type and severity of AE administer corticosteroids
 
	
 
Ensure adequate evaluation to confirm etiology and/or exclude other causes
 

	Grade 3	Withhold or discontinue based on the type of event. Events that		

		require discontinuation include and not limited to: Gullain-Barre Syndrome, encephalitis		
	Grade 4 or recurrent Grade 3	Permanently discontinue		

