
1. Withhold or permanently discontinue pembrolizumab is at the discretion of the investigator or treating physician.
 
NOTE: For participants with Grade 3 or 4 immune-related endocrinopathy where withhold of pembrolizumab is required, pembrolizumab may be resumed when AE resolves to <math>\leq</math> Grade 2 and is controlled with hormonal replacement therapy or achieved metabolic control (in case of T1DM).
				

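### For non-endocrine irAEs without their own row in Table 2, Table 5's Grade 3 and 4 dosing instruction is laxer than Table 2's catch-all row and reads as an inconsistent leftover

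*Combined protocol and SAP*

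**What the plan says.** Section 4.5 introduces the main rules: "Dose modification and toxicity management guidelines for irAEs associated with pembrolizumab are provided in Table 2". Table 2 has rows for named toxicities (pneumonitis, colitis, liver, diabetes, pituitary, thyroid, kidney, heart) and a last row for every other irAE. In that last row:

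- intolerable or persistent Grade 2 means withhold;
- Grade 3 means withhold or discontinue according to the type of event, with two neurological events named as requiring discontinuation in a list stated to be open;
- "Grade 4 or recurrent Grade 3" means permanent discontinuation.

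A note below the table treats hormone-related events differently: "For participants with Grade 3 or 4 immune-related endocrinopathy where withhold of pembrolizumab is required, pembrolizumab may be resumed when AE resolves to" Grade 2 or lower with hormonal or metabolic control.

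Section 5.3.1 offers Table 5 for irAEs that the protocol does not cover in another place. The action column is headed "Withhold/Discontinue MK-3475". Its Grade 1 row asks for no action and its Grade 2 row permits withholding. Grade 3 and Grade 4 share a row: withhold, then "Discontinue if unable to reduce corticosteroid dose to < 10 mg per day prednisone equivalent within 12 weeks of toxicity". The supportive-care column of that row adds "Steroid taper should be considered once symptoms improve to Grade 1 or less and tapered over at least 4 weeks". Table 5 says nothing about a recurrent event and nothing about resuming.

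**The concern.** Two tables in one protocol give general instructions for the same kind of event, and the second is less strict where the event is most dangerous. Table 2 makes stopping at Grade 4 unconditional. Table 5 makes withholding the default and mentions stopping only when steroids cannot be brought down in time. An investigator managing a life-threatening or recurrent severe irAE who goes to the section on supportive care for irAEs could hold the drug where Table 2 requires that it be stopped for good.

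The stake is patient safety and uniform handling of severe irAEs. Sample size, error rates and the response analysis are not involved.

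**Working it through.** No arithmetic applies; the check is a side-by-side reading.

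**Which events are in scope.** Events with their own row in Table 2 are covered there. Endocrinopathies are left out because the note to Table 2 lets them resume once controlled. Guillain-Barre syndrome and encephalitis are left out because Table 2 names them. What remains is not empty: Section 4.5 mentions skin biopsy and Section 5.3 mentions skin photography in the work-up of suspected irAEs, and Table 2 has no skin row.

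**Instructions for those events.**

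| Situation | Table 2, catch-all row | Table 5 | Reading |
|---|---|---|---|
| Grade 1 | no entry | no action | no difference |
| Grade 2 | withhold if intolerable or persistent | may withhold | can be reconciled |
| First Grade 3 | withhold or discontinue by event type; list of types to discontinue is open | withhold; stop if taper fails | Table 5 laxer for any type that Table 2 would discontinue |
| Recurrent Grade 3 | permanently discontinue | no recurrence rule; same row as first Grade 3 | Table 5 laxer |
| Grade 4 | permanently discontinue | withhold; stop if taper fails | Table 5 laxer |

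If the taper fails at 12 weeks, both tables lead to discontinuation, because Table 2's general instructions contain a similar steroid rule. The difference arises when the taper succeeds.

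**Is Table 5 a dosing rule at all?** Its column heading, "Withhold/Discontinue MK-3475", says so. Table 6 on pneumonitis uses the same heading. It states an unconditional stop at Grades 3 and 4 and a rule for a second episode. A reader who compares the two could take the absence of both from Table 5 as intended.

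**Which table governs?**

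1. If the catch-all row counts as covering all other irAEs, Table 5 has no Grade 3 or 4 event left to govern, and its row is a leftover that disagrees with the rule in force.
2. If the catch-all row does not count, Table 5 applies to exactly the events in that row and is laxer than Table 2 for them.

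The first reading is the natural one. It is supported by the limited scope given to Table 5 and by the pointers to Table 2 in Section 4.5, in the list of reasons to stop therapy in Section 4.7, and in Section 5.3, the parent of 5.3.1. None of these says in terms that Table 2 prevails where the tables differ. On either reading the row needs editing.

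**The case against.** The strongest reply is that the protocol already orders the two tables. Table 5 is residual by its own introduction, it is called a general approach, its content is introduced as recommendations, and it sits under a supportive-care heading. A row with graded actions for all remaining irAEs surely covers them. Table 5 also does not say that a failed taper is the only reason to stop, so an investigator who discontinues at Grade 4 under Table 2 breaches nothing in Table 5. Every irAE of Grade 2 or higher should be discussed at once with the company's clinical monitor, and a separate guidance document, not available here, may say more.

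Most of this stands. Table 2 is the better candidate to govern, both tables can be obeyed by following the stricter one, and the monitor is a real safeguard. It does not remove the point: a reader is sent to a table with a dosing column that omits two mandatory stops, and the discussion with the monitor does not settle which table applies.

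Three stronger readings are tempting and should not be made.

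- A reader might infer that Table 5 authorises re-treatment after a Grade 4 event. It contains no permission to resume. The resume rule, "pembrolizumab can be resumed after AE has been reduced to Grade 1 or 0 and corticosteroid has been tapered", is in Table 2, and using it here means ignoring the catch-all row of the same table. A hypothetical patient who tapers in time illustrates that mixed reading but does not show that the protocol permits it.
- A reader might tally the situations in which the tables clash. First Grade 3 cannot be scored, because Table 2's list of events to discontinue is open.
- A reader might take "See Tables 2 and 4 for details" in Section 4.6 as ranking Table 2 above Table 5. That section deals with interruptions for reasons other than treatment-related events, so its silence on Table 5 shows nothing.

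**Conclusion.** The inconsistency is real and limited. For non-endocrine irAEs without their own row in Table 2, Table 5 is laxer than Table 2 at Grade 4 and at recurrent Grade 3, and possibly at first Grade 3 for event types that Table 2 would discontinue. It is best described as a leftover row that could mislead, not as a competing rule with equal standing.

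The likelihood of harm is low, given the pointers to Table 2 and the discussion with the monitor. The documents give no basis for estimating how many patients would be affected, and no effect on efficacy analyses is claimed. The conclusion rests on the wording of the two tables and on the absence of any statement that Table 2 prevails; what the guidance document says about dosing is unknown. Because the possible consequence is serious and the correction is small, it should be made.

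**What to change.** Preferred: delete Table 5 and the sentence that introduces it in Section 5.3.1, and refer the reader to Table 2.

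Alternative: keep Table 5 and replace its Grade 3 and 4 row with three entries, plus one sentence stating that Table 2 prevails wherever the tables differ:

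- Grade 3: withhold or discontinue by event type per Table 2;
- Grade 4 or recurrent Grade 3: permanently discontinue;
- endocrinopathies: per Table 2.

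The cost is one deleted table and sentence, or one edited row and one added sentence, at the next amendment. No visits, procedures or data are added.

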**Table 6. Recommended Approach to Handling Pneumonitis**

Study drug associated pneumonitis	Withhold/Discontinue MK-3475?	Supportive Care
Grade 1 (asymptomatic)	No action	Intervention not indicated
Grade 2	Withhold MK-3475, may return to treatment if	Systemic corticosteroids are indicated. Taper as indicated.

	improves to Grade 1 or resolves within 12 weeks	
Grade 3 and Grade 4	Discontinue MK-3475	Systemic corticosteroids are indicated.

For Grade 2 pneumonitis that improves to  $\leq$  Grade 1 within 12 weeks, the following rules should apply:

- First episode of pneumonitis
  - May increase dosing interval by one week in subsequent cycles
- Second episode of pneumonitis – permanently discontinue MK-3475 if upon rechallenge subject develops pneumonitis  $\geq$  Grade 2
- Please consult the Events of Clinical Interest and Immune-Related Adverse Events Guidance Document for a more in-depth discussion of pneumonitis.

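### For immune-related events with no row of their own, Tables 2 and 5 give different drug actions at Grades 3 and 4, and no text plainly says that Table 2 prevails

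*Combined protocol and SAP*

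**What the plan says.** Two tables in the combined protocol and SAP act as the general rule for irAEs that are not named individually.

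- **Section 4.5, Table 2.** The last row covers "All other immune-related AEs". A Grade 3 event is held or discontinued according to its type; Guillain-Barré syndrome and encephalitis are named as examples, on a non-exhaustive list, of events that must lead to discontinuation. For "Grade 4 or recurrent Grade 3" the action is permanent discontinuation. The table's second general instruction adds: "Pembrolizumab should be permanently discontinued if AE does not resolve within 12 weeks of last dose or corticosteroids cannot be reduced to" 10 mg prednisone equivalent per day or less within 12 weeks.
- **Section 5.3.1, Table 5.** The introducing sentence reads: "Recommendations to managing irAEs not detailed elsewhere in the protocol are detailed in Table 5". The table has its own column on withholding or discontinuing the drug. Grades 3 and 4 share one entry: withhold, followed by "Discontinue if unable to reduce corticosteroid dose to < 10 mg per day prednisone equivalent within 12 weeks of toxicity".

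Three other places bear on which table applies. Section 4.5 says that the irAE dose-modification guidance is in Table 2. Section 4.7, item 4, cites Table 2 for stopping because of unmanageable toxicity. Section 5.3, the parent of 5.3.1, says: "Refer to Table 2 for guidelines regarding dose modification and supportive care".

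**The concern.** A Grade 4 irAE with no row of its own falls under the last row of Table 2. It can also be read as falling under Table 5, whose title presents it as the general approach to irAEs. The first forbids further drug. The second holds it and makes discontinuation depend on a failed steroid taper. A physician who turns to the supportive-care section after such an event finds a complete-looking drug-action rule there, and it is the more permissive one.

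At stake is re-exposure to pembrolizumab after a life-threatening or recurrent severe irAE in a patient for whom Table 2 says that treatment is over.

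**Working it through.** No arithmetic applies, and the plan has no figure to reproduce. The check sets the two rules side by side for irAEs without their own row, then looks for scope or precedence wording.

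**Step 1. Drug action by grade**

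| Event | Table 2, last row | Table 5 | Result |
|---|---|---|---|
| Grade 2 | Hold if intolerable or persistent | May hold | Compatible |
| First Grade 3, type calls for discontinuation | Discontinue | Hold | Opposed |
| First Grade 3, other types | Hold or discontinue by type | Hold | Compatible if held, but the limits in step 2 differ |
| Recurrent Grade 3 | Permanent stop | Hold (no recurrence rule) | Opposed |
| Grade 4 | Permanent stop | Hold | Opposed |

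For the second line, the two Grade 3 events that Table 2 names are the better protected, because an event named there is hard to describe as not covered elsewhere. Unnamed events of similar seriousness are less protected.

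**Step 2. Limits on a held patient**

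- *Steroid dose.* Table 2 requires 10 mg per day or less; Table 5 requires less than 10 mg. At exactly 10 mg, Table 5 is the stricter of the two.
- *Start of the 12 weeks.* Table 2 counts resolution of the event from the last dose and does not restate the starting point for the steroid limit. Table 5 counts from the toxicity. The documents set no upper bound on the gap between these dates: sections 4.5 and 5.3.1 both say that irAEs can appear several months after the last dose.
- *Unresolved event.* Table 2 stops permanently if the event has not resolved within 12 weeks. Table 5 has no such stop.

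**Step 3. Does withholding in Table 5 imply possible restart?** Table 5 contains no resumption wording. The inference rests on two things. A condition for discontinuing has content only if a patient who avoids it may continue. And Table 6, in the next subsection, contrasts the terms in the same way: its Grade 2 pneumonitis entry is "Withhold MK-3475, may return to treatment if" the event improves, while its Grade 3 and 4 entry is to discontinue.

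**Step 4. Which table governs?** The sentence introducing Table 5 makes that table residual, and it can be read in two ways.

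- If the last row of Table 2 counts as detailing every remaining irAE, Table 5 yields and the permanent stop applies. The Grade 3 and Grade 4 entry of Table 5 then governs nothing.
- If an irAE counts as detailed elsewhere only when it has its own row, Table 5 applies and sets aside the permanent stop.

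The pointers in 4.5, 4.7 and 5.3 support the first reading. None says what to do when the tables differ.

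**The case against.** The strongest reply is that the text already settles the matter. Table 5 is confined to irAEs not dealt with elsewhere, Table 2 deals with all the others, and three sections send the reader to Table 2. On the literal reading, Table 5 is redundant and harmless. Table 5 also offers recommendations, and section 5.3.1 requires immediate discussion of any irAE of Grade 2 or higher with the clinical monitor.

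Much of this stands. A reader might infer that the protocol is silent on which table governs; the documents do not support that, because the scope wording and the pointers favour Table 2. A reader might also take restart under Table 5 as written text; it is implied. What remains is that none of these passages is an express precedence rule. The reading that leaves Table 5 with a function is a natural one, and the monitor is not told which table to apply. A permanent-stop rule after a life-threatening event should not depend on inference.

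A further tempting step is to say that the conflict distorts the interim futility decision, through the 12-week evaluability rule in section 11.1. That would need a qualifying event before week 12 in a patient exactly at a boundary, and a rule on whether a held patient counts as on treatment, which the protocol does not define. The documents do not support it as a material effect. Nor do they specify a count of permanent stops as a safety analysis: sections 7.1 and 11.3 plan adverse event rates, laboratory changes and toxicity grades. The 10 mg limit in section 5.1 does not help choose between the tables, because it concerns steroid replacement therapy.

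**Conclusion.** Wrong as written: two safety rules conflict. For irAEs without their own row, the tables prescribe opposed actions at Grade 4, at recurrent Grade 3, and at Grade 3 events whose type calls for discontinuation. For a first Grade 3 event that is held, three limits differ: the steroid dose, the stated start of the 12 weeks, and the stop for an unresolved event. Events with their own row in Table 2 are outside this point.

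The conclusion assumes that withholding in Table 5 leaves restart open, and that some physicians would read its scope sentence as covering events without their own row. The better reading favours Table 2, so the defect is the lack of a plain statement combined with a contrary entry. The documents give no event rate from which to estimate how many patients would be affected. The primary endpoint, the alpha level and the sample size are not touched. The change should be made on patient-safety grounds alone.

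**What to change.** In section 5.3.1, Table 5, replace the Grade 3 and Grade 4 entry in the withhold/discontinue column with: *Follow Table 2, row All other immune-related AEs, and its General instructions.* After the sentence that introduces Table 5, add: *If Table 5 and Table 2 differ on withholding, restarting or discontinuing, Table 2 prevails.*

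The two changes overlap on purpose. The cell removes the contrary instruction where a physician would read it, and the sentence covers any other difference between the tables. Table 2 and the supportive-care column of Table 5 stay as they are. Deleting Table 5 would also remove the conflict, but would lose its supportive-care advice.

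The cost is one table cell and one sentence in an amendment, with no added visits, tests or patients.
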